7.4 Criteria for withdrawal / discontinuation of participants

Participants will be withdrawn from the study immediately if there are any concerns about the participants' safety. Participants can also choose to withdraw from the study at any time, and are not required to provide their reason for withdrawing from the study. Coded data acquired before withdrawal will be analyzed.

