4.5 Safety Objectives

The study aims to assess short- and long-term safety of SleepExpert and its tolerability in terms of incidence of sleep- and mental-health related side effects and use of sleep medication.

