6.2.3 Other methods of minimising bias

- The primary applicant is a staff member at the sleep clinic of the University Psychiatric Services Bern. The resources at this established, specialized sleep clinic will ensure that included patients are carefully diagnosed, i.e. that only patients fulfilling the defined eligibility criteria will be included. This ensures generalizability of the results to the intended population.
- Study attrition and reasons for dropout will be carefully documented throughout the study period.
- An intention to treat analysis will be provided since a per-protocol analysis may result in biased effects if many patients drop out due to (perceived) inefficacy.
- The outcome measures are widely used, valid, and reliable measures that have been recommended by experts for the research assessment of insomnia (Buysse, Ancoli-Israel, Edinger, Lichstein, & Morin, 2006).
- Therapists will be experienced, well-trained, and supervised.
- The trial will be registered in a publicly accessible database before recruitment of the first subject. Hypotheses and the analysis plan will be made publicly available. This precludes that the analysis plan is changed after inspection of the data ("fishing for significances").

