8.5 Data Collection and Follow-up for withdrawn participants

If a patient withdraws consent for further study participation, the data collected up to the time point of withdrawal will be included in the study and no further data will be collected. The data of withdrawn participants will not be anonymized but will remain coded after analysis of the data set.

For participants who discontinue the study intervention but do not withdraw from participation in the study, study visits and data collection will continue in the same way as for non-withdrawn participants.

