9.2.5 Assessments in participants who prematurely stop the study

For participants who discontinue the study intervention but do not withdraw from participation in the study, study visits and data collection will continue in the same way as for non-withdrawn participants.

Dropouts before start of treatment (i.e. non-starters) will be replaced by recruitment of new participants.

Patients who started the intervention but who were prematurely withdrawn from the study will not be replaced by newly enrolled patients.

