10.3 Medical Device Category A studies

Device deficiencies and all **adverse events (AE)** including all **serious adverse events (SAE)** are collected, fully investigated, and documented in the source document and appropriate case report form (CRF) during the entire study period, i.e. from patient's informed consent until the last protocol-specific procedure. Documentation includes dates of event, treatment, resolution, assessment of seriousness, and causal relationship to device and/or study procedure [ISO 14155, 6.4.1.].

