10.3.1 Foreseeable adverse events and anticipated adverse device effects

Potential adverse events are transitional worsening of the sleep disorder and / or the mental disorder, daytime tiredness and daytime sleepiness. No SAE that could be related to the investigational device or study procedures are expected during this clinical trial.

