11.5 Handling of missing data and drop-outs

Dropouts before start of treatment (i.e. non-starters) will be replaced by recruitment of new participants. Multiple imputation will be used in case data are not available for more than 5-10% of the sample.

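### Section 7.4 answers any safety concern with withdrawal from the whole study, so the remaining ISI and adverse-event assessments of these patients have no provision

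*Combined protocol and SAP*

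**What the plan says.** Section 7.4 (Criteria for withdrawal / discontinuation of participants) gives a single response to a safety concern: "Participants will be withdrawn from the study immediately if there are any concerns about the participants' safety". It adds that participants may leave by their own choice and that coded data obtained before withdrawal are analysed. It does not mention stopping only the intervention, and it does not mention later data.

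Section 8.5 has two rules. If consent is withdrawn, earlier data are kept and collection ends. Otherwise: "For participants who discontinue the study intervention but do not withdraw from participation in the study, study visits and data collection will continue". Section 9.2.5 repeats the second rule and then names a separate group: "Patients who started the intervention but who were prematurely withdrawn from the study will not be replaced by newly enrolled patients". It sets no assessments for that group.

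Section 10.3 collects adverse events "from patient's informed consent until the last protocol-specific procedure". Section 10.3.1 lists what is foreseen: "Potential adverse events are transitional worsening of the sleep disorder and / or the mental disorder, daytime tiredness and daytime sleepiness". The safety objective in 4.5 is broad: "The study aims to assess short- and long-term safety of SleepExpert and its tolerability". On missing data, 11.5 says: "Multiple imputation will be used in case data are not available for more than 5-10% of the sample".

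**The concern.** The protocol has the right status for a patient who should stop treatment but can still be followed, and 7.4 does not use it for the cases where it matters most. Three things are at stake.

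- **Primary outcome.** Worsening sleep and daytime impairment are what the ISI measures (9.2.1). A patient withdrawn because of them leaves with a poor outcome that is not recorded at later visits. The rule applies to both arms, but the SleepExpert group session usually shortens time in bed (8.1.1), whereas the control app only records sleep (3.6). More safety withdrawals under SleepExpert are therefore plausible, though not shown. Section 6.2.3 promises an intention-to-treat analysis because "a per-protocol analysis may result in biased effects if many patients drop out due to (perceived) inefficacy". The rule in 7.4 creates avoidable dropout of a similar kind.
- **Safety.** Adverse events are asked about at T0 to T4 (9.2.4.1) and their frequencies are compared by chi-square tests, with no stated allowance for length of follow-up (Safety analysis, 11.4.4). A patient withdrawn after T2 has no scheduled questioning at T3 or T4. That follow-up is lost in the patients most relevant to the long-term safety objective.
- **Next step.** A large confirmatory trial follows if the pilot is encouraging (11.2), so a favourable bias would carry forward.

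**Working it through.** **Reading the sections together.** Section 7.4 withdraws the patient from the study. The continued visits in 8.5 and 9.2.5 require that the patient has not withdrawn from participation, so a 7.4 case does not qualify. The rule in 8.5 that ends collection concerns withdrawn consent only. For an investigator's safety withdrawal the protocol is therefore silent rather than prohibitive. Table 1 and sections 8.5, 9.2.5, 9.3.2, 10.3, 11.4.4 and 11.5 contain no early-termination visit, no remaining ISI schedule and no later adverse-event schedule for these patients. The ISI visits lost depend on timing: all four follow-up scores if exit is before T1, three between T1 and T2, two between T2 and T3, one between T3 and T4.

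**Inputs.** From the documents: 60 patients in total; ISI at T0 and weeks 1, 2, 12 and 26; a mixed model of the four follow-up scores with a baseline ISI covariate and one intervention effect (11.4.2). The plan gives no withdrawal rate, ISI SD or size of worsening, so there is no figure of its own to reproduce on this point. Assumed: 30 per arm; 5%, 10% or 15% of the SleepExpert arm withdrawn for safety (1.5, 3 or 4.5 patients); ISI 4, 6 or 8 points worse than it would otherwise be; within-patient correlation 0.5; SD 5.

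**Bias formula.** Let p1 and p0 be the withdrawn shares under SleepExpert and control, d the worsening, and f the fraction of d, averaged over the four follow-up visits, that the analysis does not recover. With the same d and f in both arms:

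bias in favour of SleepExpert = (p1 − p0) × d × f

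**Finding f.** After adjustment for baseline at correlation 0.5, the residual variance share is 1 − 0.5² = 0.75 and the residual covariance is 0.5 − 0.5² = 0.25, so the residual correlation is 0.25/0.75 = 1/3. A T1 score that is d points worse leads the model to expect d/3 at each later visit.

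- A. No follow-up ISI before exit, worsening lasts: true mean d, recovered 0, so f = 1.
- B. T1 taken but not yet worse, worsening lasts from T2: true mean 3d/4, recovered 0, so f = 0.75.
- C. T1 shows it, worsening lasts: true mean d, recovered (d + 3 × d/3)/4 = d/2, so f = 0.5.
- D. No follow-up ISI before exit, gone by T3: true mean 2d/4 = d/2, recovered 0, so f = 0.5.
- E. T1 shows it, gone by T3: true mean d/2, recovered d/2, so f = 0.

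The figures in brackets come from a simulation of the planned model with visit terms added and 60,000 per arm, so that only bias shows.

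| Case | p0 = 0: 5%, 4 points | p0 = 0: 10%, 6 points | p0 = 0: 15%, 8 points | p0 = p1/2: 10%, 6 points |
|---|---|---|---|---|
| A | 0.20 (0.19) | 0.60 (0.61) | 1.20 (1.18) | 0.30 (0.31) |
| B | 0.15 (0.15) | 0.45 (0.45) | 0.90 (0.89) | 0.225 (0.22) |
| C | 0.10 (0.10) | 0.30 (0.29) | 0.60 (0.58) | 0.15 (0.13) |
| D | 0.10 (0.09) | 0.30 (0.30) | 0.60 (0.60) | 0.15 (0.15) |
| E | 0 (about 0) | 0 (about 0) | 0 (about 0) | 0 (about 0) |

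With p0 = p1 every entry is 0. On the assumed SD of 5, the design effect d = 0.65 is 3.25 ISI points. A bias of 0.3 is then 9% of it, 0.6 is 18%, and 0.13 is 4%.

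**Imputation trigger.** 1.5/60 = 2.5%, 3/60 = 5%, 4.5/60 = 7.5%. Safety losses in one arm may not on their own pass the 5–10% threshold in 11.5.

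**Power.** The loss is small. For d = 0.65 and a two-sided t test, power is 0.697 with 30 per arm and 0.673 with three SleepExpert patients lost. (The total of 60 gives 0.80 only for a one-sided test; that is a separate matter and does not affect this point.)

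**The case against.** The best reply is that the protocol is ambiguous rather than wrong. The only sentence that ends data collection concerns withdrawn consent. Not withdrawing from participation could be read as the participant's own act, so a patient taken off SleepExpert by the investigator, with consent intact, might fall under the continue-visits rule. Section 9.2.5 is headed as covering people who stop early, and its only assessment rule is to continue.

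The trigger may also be rare. The foreseen effects are transient, nurses see patients twice a week and can adapt the sleep window (8.1.1), and such cases need not reach 7.4. What is left, for example suicidality or psychotic worsening, could arise in either arm. The size is wholly assumed, and the case nearest to the documents' description (transient, with T1 recorded) gives about 0. Other losses over 26 weeks count towards the imputation threshold too. An open adverse event may be followed to resolution under 10.3. And this is a pilot.

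Much of this stands: the direction is inferred, the size may be zero, and the event that prompted withdrawal may well be followed. The reading of 8.5 does not stand. Section 7.4 says the patient is withdrawn from the study and speaks only of earlier data, and 9.2.5 treats those withdrawn from the study as a different group. Even on the kindest reading, staff have two unreconciled instructions when a patient deteriorates. Reaching the imputation threshold would help little, because standard imputation cannot restore a worsening that was never recorded.

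**Conclusion.** The point holds. As written, a patient whose worsening is judged a safety concern leaves the study, and nothing provides for the remaining scheduled ISI and adverse-event assessments. The possible bias in the primary estimate runs from 0 to 1.2 ISI points in favour of SleepExpert on the assumed inputs. The top of that range needs 15% withdrawn, 8 points of lasting worsening, no control withdrawals and no follow-up score before exit. With half as many control withdrawals, the mid-case is about 0.13 points if T1 shows a lasting worsening and 0.3 if no follow-up score was taken. The loss of scheduled safety follow-up to week 26 does not depend on those inputs beyond there being such a withdrawal. Confidence in the practical importance is medium. This should be changed, but it does not undermine the trial.

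**What to change.** Amend 7.4 so that a safety concern leads to an immediate decision to stop or adapt the study intervention. The participant stays in the study and completes the remaining T1–T4 assessments and adverse-event follow-up under 8.5 and 9.2.5, unless consent to data collection is withdrawn or the assessments themselves are the concern. Record the date and reason for stopping the intervention separately from study exit; 6.2.3 already commits to documenting reasons for dropout.

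Treatment is stopped just as quickly as now. The cost is a wording amendment and a few more questionnaires, which are already scheduled and can be entered remotely by eCRF after discharge (12.1.1). The estimate may become slightly less favourable to SleepExpert.

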8. STUDY INTERVENTION

8.1 Identity of Investigational Products (treatment / medical device)

8.1.1 Experimental Intervention (treatment / medical device)

General information

Both groups will receive psychiatric inpatient treatment-as-usual (TAU). TAU will be provided according to current treatment guidelines for the respective mental disorders. Within the trial period, TAU will be delivered as usual in the respective hospitals. No restrictions with regard to pharmacotherapy, psychotherapy, or any other inpatient therapy or subsequent outpatient care will result from participation in the SleepExpert trial.

TAU will consist of the following interventions: daily visit by a physician or psychologist, if necessary individualized pharmacological treatment according to current guidelines, individualized disorder-specific psychotherapy according to current guidelines, daily contact with a psychiatric nurse, ergo therapy, and other group therapies according to a personalized schedule (e.g. music therapy, art therapy, relaxation therapy, etc.). The duration of the inpatient stay will be adapted to the progress of the individual patient and will vary from participant to participant. The duration of the stay is typically between one to eight weeks, exceptions are possible.

The TAU plus SleepExpert group will receive a specific treatment for insomnia. This treatment will consist of the following three phases:

- 1) a face-to-face treatment initiation guided by a medical doctor/ psychologist in a group format (1 hour),
- 2) self-managed implementation of behavioral changes assisted by an online application ("Become your own SleepExpert") and coached by nurses (two individual contacts per week of about 5 min duration), and
- 3) self-management by the patients assisted by the same online application after discharge from the hospital.

The treatment initiation will be a psycho-educative group session held by a physician or psychologist. During this group session, basic information about sleep regulation will be provided, including the two components i) homeostatic build-up of sleep pressure as a function of prior wake time, and ii) relevance of individual circadian sleep-wake preferences. At the end of the group session, an individual sleep window (duration of bed time and timing) will be worked out with every patient. In most patients, the time in bed is shortened and 'lights-off' is delayed compared to the previous behavior with the aim of increasing sleep pressure and moving sleep time into a physiological time frame. The background is that patients with insomnia often increase their time in bed in order to catch more sleep - which, however, is actually detrimental for sleep quality. The online application will be introduced in this group therapy session. In the second phase of the treatment program, nurses will regularly meet with the patients to discuss their sleep behavior. Patients will be assisted in keeping or, if necessary, adapting their prescribed sleep window, and will receive advice, motivation and assistance in using the application. Patients will learn how to use the application in order to document and adjust their sleep behavior. In the third phase (defined as starting from discharge from the psychiatric ward), patients will use the online application in self-management to keep optimizing their sleep behavior. All patients, i.e. the TAU plus sleep monitoring and TAU plus SleepExpert group will have an individual appointment with a sleep expert (physician or psychologist) after completion of the study, i.e. after 6 months, in which the gathered information (sleep diaries) will be discussed and individualized further diagnostics and treatments, if needed, will be initiated.

Online application

The online application 'Become your own SleepExpert' is currently developed in cooperation with Prof.

[name], University of Bern. [name] has a longstanding experience in the field of internet- and app-based prevention and treatments of mental problems and disorders. His publication record includes a multitude of studies investigating the efficacy of online treatments for different mental health problems and disorders, including anxiety, depression, insomnia, adjustment problems and self-criticism (e.g., Krieger et al., 2019; Moser et al., 2019; Schuster et al., 2019; Weisel et al., 2019).

8.1.2 Control Intervention (standard/routine/comparator treatment / medical device)

Patients in the control group will receive the same TAU as the experimental group (see 8.1.1).

In addition, patients in the control group (TAU plus sleep monitoring) receive a smartphone app (sleep monitoring). No further interventions will be provided through this app.

8.1.3 Packaging, Labelling and Supply (re-supply)

Not applicable.

8.1.4 Storage Conditions

Not applicable.

8.2 Administration of experimental and control interventions

8.2.1 Experimental Intervention and Control Intervention

This chapter can also be merged with chapter 8.1.1.

8.2.2 Control Intervention

This chapter can also be merged with chapter 8.1.2.

8.3 Dose / Device modifications

Not applicable.

8.4 Compliance with study intervention

Adherence will be monitored using subjective patient data from the SleepExpert application. In the application, patients will log their bed times and rise times as well as subjective sleep times.

Treatment contamination (i.e., patients in the TAU plus sleep monitoring group learning about details of the SleepExpert intervention) will be prevented by cluster randomization of wards. One entire ward will be randomized to one of the conditions. The other ward will receive the remaining condition (preventing that both wards get the same condition). Patients in the control group will not get in close contact with patients in the intervention group. Additional measures to increase adherence include a start of the intervention in the inpatient setting along with individual coaching by nurses and a helpdesk that can be called in case of problems with the program. Please note that no further extensive contacts are planned to increase generalizability of the program after completion of the study.

8.5 Data Collection and Follow-up for withdrawn participants

If a patient withdraws consent for further study participation, the data collected up to the time point of withdrawal will be included in the study and no further data will be collected. The data of withdrawn participants will not be anonymized but will remain coded after analysis of the data set.

For participants who discontinue the study intervention but do not withdraw from participation in the study, study visits and data collection will continue in the same way as for non-withdrawn participants.

8.6 Trial specific preventive measures

No specific preventive measures will be taken in this trial. There will be no restrictions to treatment or daily life related to this trial.

8.7 Concomitant Interventions (treatments)

All concomitant treatments / interventions are permitted and will be recorded in the CRF. The aim of this trial is to implement SleepExpert into the clinical routine care for patients with severe mental disorders, thus no artificial / trial-specific restrictions will be applied. Careful documentation of concomitant treatment will prevent biasing of the results.

8.8 Medical Device Accountability

Not applicable, patients will use the trial-specific web applications from their own devices.

8.9 Return or Destruction of Medical Device

Not applicable.

9. STUDY ASSESSMENTS

9.1 Study flow chart(s) / table of study procedures and assessments

The overall planned study duration is 2.5 years. Patients will first be screened and assessed for eligibility. Eligible patients who signed the informed consent form will undergo a first assessment (T0) and then participate in the intervention. Additional assessments will be made one, two, 12, and 26 weeks after the start of the intervention. A plan of each patients' schedule within the study is outlined in table 1 which is illustrated in chapter 1.1.

9.2 Assessments of outcomes

9.2.1 Assessment of primary outcome

The ISI is a valid, reliable and change-sensitive self-rating questionnaire that is widely used as an outcome measure in clinical trials in insomnia research (Buysse et al., 2006). It ranges from 0 to 28 with higher values indicating more severe problems. A self-rating questionnaire in contrast to objective sleep measures such as polysomnography or actigraphy is reasonable and widely accepted for measuring insomnia severity because insomnia is defined on the basis of subjective sleep dissatisfaction (American Psychiatric Association, 2013; Medicine, 2014; Organization, 2004) and objective measures often deviate from this perception (Harvey and Tang, 2012). An advantage of the ISI, compared to a sleep diary, is that it combines different aspects of insomnia such as sleep onset difficulties, sleep maintenance difficulties, and daytime impairment in one summary score. For more information, see chapter 5.1.

9.2.2 Assessment of secondary outcomes

The BSI is a brief version of the Symptom Checklist 90 (SCL-90) (Derogatis et al., 1976). It shows high correlation with the long version and has a good test-retest reliability (Derogatis and Melisaratos, 1983). We chose the BSI because it is an efficient measure of general mental health. In our sample, patients will suffer from different mental disorders including but not limited to depression, psychosis, anxiety and substance abuse. In addition, we expect that many patients suffer from more than one mental disorder (comorbidity). A general measure, beyond the severity of specific disorders, is thus needed to picture changes in general mental health. For more information, see chapter 5.2

